5.4. Dose interruption and adjustment of study drugs

Dose interruption and adjustment of sunitinib will be carried out according to guidelines in the approved package insert.

If AE occurs, the investigator can determine interrupt administration of DCC-2618 (ripretinib, ZL-2307) or adjust its dose (that is, dos reduction). If dose adjustment is required for other reasons, it is necessary to discuss with the sponsor and make a decision. Interruption duration should not be more than 28 consecutive days.

For sunitinib and DCC-2618 (ripretinib, ZL-2307), department visit and assessment should be continued during dose interruption according to Table 1 (Schedule of Assessments). If administration is resumed after dose interruption, the investigator must continue administration according to the source visit schedule from C1D1 (that is, calculate the number of days of cycle continuously and not discontinue calculation due to dose interruption). If dose interruption is more than 28 days, treatment with the study drug will be terminated in this patient. If the regimen used by the patient is 4-week administration followed by 2-week withdrawal, the 28-day time limit also includes the 2-week withdrawal.

5.4.1. Interruption of the study drug due to planned medical procedure

According to the approved package insert, sunitinib should be interrupted if major surgical procedure is required.

For DCC-2618 (ripretinib, ZL-2307), surgery performed in patients during the study, surgical range and postoperative healing speed should be considered. It applies to the following guidelines:

- Scheduled minimally invasive surgery: 3 days before and after the surgery, DCC-2618 (ripretinib, ZL-2307) must be discontinued for 3 days.
- Scheduled major surgery: 5 days before and after the surgery, DCC-2618 (ripretinib, ZL-2307) must be discontinued for 5 days.
- Unscheduled/emergent surgery: DCC-2618 (ripretinib, ZL-2307) must be discontinued immediately and resumed according to requirements of the above minimally invasive and/or major surgery.

5.4.2. Dose interruption and adjustment of DCC-2618 (ripretinib, ZL-2307) caused by adverse events

If AE occurs, the investigator can determine to discontinue DCC-2618 (ripretinib, ZL-2307) or reduce its dose at any time according to guidelines in Table 6, Table 7 Table 8, Table 9 and Table 10. It is necessary to discuss dose reduction with the sponsor in advance as far as possible. If DCC-2618 (ripretinib, ZL-2307) is resumed after interruption, the patient should use the drug according to the former administration schedule.

If any patient needs to use the drug at a dose lower than 50 mg QD, or if dose for the patient has been reduced and progressive disease is confirmed by independent radiologic reviewers, the patient must discontinue the study drug and receive end of treatment (EOT) visit and safety follow-up visit. In addition, OS of the patient must be followed up.

Table 5: Dose reduction steps of DCC-2618 (ripretinib, ZL-2307)

Initial dose of DCC-2618	The 1st dose reduction	The 2nd dose reduction
150 mg QD	100 mg QD	50 mg QD

If AE is recovered to grade 1 or baseline level, the dose should be increased for the patient. It is necessary to increase the dose for the patient to the dose level at AE occurrence. If dose level is reduced to the first dose reduction level and AE is recovered to grade 1 or baseline level, the patient can resume the drug according to the starting dose level. If the patient reduces the dose twice continuously and AE is recovered to grade 1 or baseline level after the second dose reduction, the drug should be administered at the first dose reduction level which should be maintained for at least 1 cycle continuously before increasing the dose to the starting dose level.

If an AE leads to dose adjustment and is not recovered to grade 1 or baseline level within 1 cycle (42 days), DCC-2618 (ripretinib, ZL-2307) must be discontinued, unless the investigator considers the event is not clinically significant. In such case, feasibility of resuming the drug at a dose reduction level should be judged after consulting the sponsor.

Table 6: Principle of dose adjustment of DCC-2618 (ripretinib, ZL-2307) due to skin toxicity (except Alopecia) and joint pain/myalgia

Toxicity Grade*	Dose Adjustment Principle	
Grade 1	Adopt supportive treatment of study institution and continue DCC-2618 at the current dose	
Grade 2	Adopt supportive treatment of study institution and continue DCC-2618 at the current dose If the event is not improved within 7 days, DCC-2618 will be discontinued If the event is recovered to grade 1 or baseline level within 7 days, DCC-2618 will be resumed at the same dose level	
	 If the event is recovered to grade 1 or baseline level after 7 days, DCC-2618 will be resumed at a reduced dose level If the event recurs, DCC-2618 will be resumed at a reduced dose after the event is 	

Toxicity Grade*	Dose Adjustment Principle
	recovered to grade 1 or baseline level, regardless of the time to recovery • If the event maintains grade 1 or baseline level for at least 1 administration cycle (42 days) after dose reduction, it can be considered to increase the dose of DCC-2618 by a dose level
Grade 3	 Adopt supportive treatment of the study institution Withhold DCC-2618 for at least 7 days or until the event resolves to grade 1 or baseline level (28 days at most). Resume DCC-2618 at a reduced dose If the event maintains grade 1 or baseline level for at least 1 administration cycle (42 days) after dose reduction, it can be considered to increase the dose of DCC-2618 by a dose level
Grade 4	Discontinuing DCC -2618.
Grade: any	Stevens-Johnson syndrome: If patients have developed Stevens-Johnson syndrome (SJS)/hypersensitivity reaction during treatment period, the DCC-2618 must be discontinued permanently. Patients should be transferred to hospital immediately to receive clinical assessment and supportive care/treatment accordingly. DCC-2618 should not be resumed due to risks of SJS/hypersensitivity reaction recurrence. It is not suggested to use other similar drugs (TKI for GIST) to avoid SJS recurrence because similar reaction occurred during regorafenib treatment in a patient who was diagnosed with SJS during DCC-2618 treatment.
* The severity of	AEs outside the CTCAE is confirmed according to Table 12.

Table 7: Principle of dose adjustment of DCC-2618 (ripretinib, ZL-2307) due to hypertension

Toxicity Grade	Dose Adjustment Principle
Grade 1	
Prehypertension (systolic blood	Monitor BP continuously
pressure 120-139 mmHg or diastolic	Continue DCC-2618 administration at the current dose level
blood pressure 80-89 mmHg)	
C I. 2	Adopt antihypertensive therapy to make diastolic blood
Grade 2	pressure ≤ 90 mmHg or systolic blood pressure ≤ 140 mmHg
Systolic blood pressure 140 - 159	Continue DCC-2618 administration at the current dose level
mmHg or diastolic blood pressure 90	
- 99 mmHg or elevation > 20 mmHg	If a 20 mmHg symptomatic blood pressure increased occurs
(diastolic blood pressure) with	(diastolic blood pressure), DCC-2618 should be discontinued
accompanying symptoms or blood	until symptom resolved and diastolic blood pressure ≤ 90
pressure > 140/90 mmHg (previous	mmHg
normal blood pressure)	DCC-2618 is resumed at the same dose level
Grade 3	Adopt antihypertensive therapy to make diastolic blood
Systolic blood pressure ≥ 160 mmHg	pressure ≤ 90 mmHg or systolic blood pressure ≤140 mmHg
or diastolic blood pressure ≥ 100	Starting hypotensor treatment
mmHg or more than one hypotensor	and/or
or more intensive treatment required	Increase the dose of current hypotensor
	and/or
	Add other hypotensor
	If symptomatic, DCC-2618 should be discontinued until diastolic blood pressure ≤ 90 mmHg and/or systolic blood pressure ≤ 140 mmHg and symptom resolved
	DCC-2618 is resumed at the same dose level
	If BP is uncontrollable after adding new drug or more intensive treatment, DCC-2618 will be reduced by a dose level
	If grade 3 hypertension occurs after dose reduction of DCC-2618 and antihypertension therapy, DCC-2618 will be reduced by a dose level again
Grade 4	Adopt antihypertension therapy according to guidelines for the
Life-threatening (such as malignant	treatment of hypertension
hypertension, transient or	
permanent nerve damage or	Discontinuing DCC -2618.
hypertensive crisis)	
nyper tensive erisis)	

BP = Blood pressure

*If BP is controllable within at least 28 days, the investigator may increase the dose of DCC-2618 again according to conditions.

Table 8: DCC-2618 Dose Modifications for Left Ventricular Systolic Dysfunction

Toxicity Grade	Management Guideline
Any Grade 3 or 4	Permanently discontinue DCC-2618

Table 9 DCC-2618 Dose Modifications for Isolated Bilirubin Increased

Toxicity Grade	Management Guideline
Grade 2	Interrupt DCC-2618 until toxicity resolves to Grade 1 or baseline (maximum 28 days); resume DCC-2618 at 100 mg.
Grade 3 or 4	Interrupt DCC-2618 until toxicity resolves to Grade 1 or baseline (maximum 28 days); otherwise permanently discontinue DCC-2618. If the event returns to Grade 1 or baseline, resume DCC-2618 at 100 mg. If the reduced dose is tolerated without recurrence of the event for at least 28 days, consider re-escalating DCC-2618. If Grade 3 or higher toxicity recurs, discontinue DCC-2618 permanently.

Table 10: Principle of dose reduction of DCC-2618 (ripretinib, ZL-2307) due to treatment-related adverse events not mentioned above

Toxicity Grade	Dose Adjustment Principle ¹
Any grade 3 or 4 events	Discontinue DCC-2618 until the event is relieved to grade 1 or baseline level. After the event is relieved to grade 1 or baseline level, DCC-2618 should be administered at a lower dose level. If the patient tolerates the reduced dose and the event doesn't occur within at least 28 days, DCC-2618 can be increased to the former dose level again.
Asymptomatic/not clinically significant grades 3 or 4 laboratory abnormality (including CPK and lipase) lasting ≤ 10 days	Monitor clinical symptoms closely and continue administration of DCC-2618 at the current dose level. Carry out laboratory test within 10 days.
Asymptomatic/not clinically significant grades 3 or 4 laboratory indicator abnormal (including CPK and lipase) lasting > 10 days	Monitor clinical symptoms closely; if it is a grade 4 event, discontinue DCC-2618 until the event is recovered to grade 3; after the event is recovered to grade 3, resume DCC-2618 at the current dose level or reduce to a lower dose level by he investigator according to conditions after discussing with the sponsor. For asymptomatic grades 3 or 4 lipase or CPK increase, dose
Clinically significant grade 3 or 4	interruption is not required; Discontinuing DCC-2618 dosing. If the investigator considers

laboratory abnormality (including	that resuming DCC-2618 meets the patient's best interest, it is
CPK and lipase)	necessary to discuss with the sponsor to confirm whether to
	resume the drug.

CPK = Creatine phosphokinase

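### Section 5.4.2 directs ripretinib re-escalation on recovery with no wait after a first reduction or at 50 mg, but the dose tables make it optional after 28 or 42 days; Table 9's fixed 100 mg restart also misfits patients already reduced

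*Combined protocol and SAP*

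**What the plan says.** Table 5 sets three ripretinib levels: 150, 100 and 50 mg once daily. The text of Section 5.4.2 after Table 5 then covers going back up. Its general rule is "If AE is recovered to grade 1 or baseline level, the dose should be increased for the patient", followed by "It is necessary to increase the dose for the patient to the dose level at AE occurrence". After a first reduction and recovery, "the patient can resume the drug according to the starting dose level", with no waiting time. After two reductions and recovery, "the drug should be administered at the first dose reduction level which should be maintained for at least 1 cycle continuously" before a return to 150 mg. That one-cycle hold is at 100 mg. No wait is stated at 50 mg.

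The tables in the same section use recovery to grade 1 or baseline, or blood pressure control in Table 7, but treat re-escalation differently. Table 6 (skin, joint and muscle toxicity) lets it be considered, by one level, after at least 42 days. The Table 7 footnote (hypertension), the Table 9 row for grade 3 or 4 bilirubin and the general grade 3 or 4 row of Table 10 allow it after at least 28 days. The Table 9 grade 2 row says nothing on it.

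Both Table 9 rows restart at 100 mg whatever dose the patient was taking. Section 5.4.2 also sets a floor, with discontinuation as the consequence: "If any patient needs to use the drug at a dose lower than 50 mg QD".

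**The concern.** A site can take two different instructions from one section for the same recovered patient. The body text reads as an obligation triggered by recovery. The tables read as an option that opens only after the patient has shown weeks of tolerance at the lower dose. Section 5.4.2 points sites to Tables 6 to 10 for stopping or reducing the drug. It does not point to them for raising the dose again, and it states no order of precedence. A site following the body text could return a patient early to the dose at which the toxicity occurred.

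Table 9 has a separate problem. A fixed restart dose works as a reduction only if the patient was on 150 mg. For a patient already reduced for another reason, the row gives either the same dose or a higher one after a bilirubin event. What is at stake is consistent and safe dosing across sites.

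**Working it through.** The plan states no figure to reproduce. The check sets the rules side by side and then works out the size of the difference.

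**1. Re-escalation rules**

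| Place | Duty or option | Minimum wait stated |
|---|---|---|
| 5.4.2, general sentences | duty | none |
| 5.4.2, after a first reduction (100 to 150 mg) | option | none |
| 5.4.2, after a second reduction (50 to 100 mg) | duty | none |
| 5.4.2, later step (100 to 150 mg) | not specified | 1 cycle (42 days) |
| Table 6, grade 2 and grade 3 | option | 42 days |
| Table 7, footnote | option | 28 days of blood pressure control |
| Table 9, grade 2 | silent | silent |
| Table 9, grade 3 or 4 | option | 28 days |
| Table 10, general grade 3 or 4 row | option | 28 days |

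**2. Timing after one reduction.** Take a grade 2 skin event at 150 mg that recovers late. Table 6 says "If the event is recovered to grade 1 or baseline level after 7 days, DCC-2618 will be resumed at a reduced dose level", so the patient restarts at 100 mg. Recovery came before the restart, so the condition in 5.4.2 for going up is already met on the first day at 100 mg. The earliest return to 150 mg is therefore:
- body text: no minimum, effectively 0 days;
- Table 6: 42 days;
- under the same logic, Table 9 grade 3 or 4 and Table 10: 28 days.

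The dose ratio over that interval is 150/100 = 1.5. The modelled combined AUC in Table 4 gives 33,583/22,389 = 1.50. This only restates dose proportionality.

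**3. Timing after two reductions.** The earliest return from 50 to 150 mg is:
- body text alone: 0 + 42 = 42 days;
- Table 6 wait at 50 mg, then the 5.4.2 hold at 100 mg: 42 + 42 = 84 days;
- a 28-day table wait at 50 mg, then the same hold: 28 + 42 = 70 days.

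The last two figures assume that the table wait and the 5.4.2 hold are served one after the other, which the protocol does not say.

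**4. Table 9 restart against the dose at onset**
- From 150 mg: 100/150 = 0.67.
- From 100 mg: 100/100 = 1.0.
- From 50 mg: 100/50 = 2.0.

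**5. What a longer stay at 100 mg costs.** Sections 1.5.2.1.3 and 1.5.2.1.4 predict 93.6% of patients above the exposure threshold at 150 mg and 87.9% at 100 mg, a difference of 93.6 − 87.9 = 5.7 percentage points. The shares below the threshold are 6.4% and 12.1%.

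**The case against.** The best defence is that the general sentences follow the dose-reduction steps and speak of increasing the dose, which presupposes a reduction. They are then rules for re-escalation, and restarting lower under a table is simply the step before. This is the natural reading, and it stands. A reader might infer that every table row restarting at a reduced dose contradicts 5.4.2, but the documents do not support that. The conflict concerns when, and whether, the dose goes back up.

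One can go further. The first-reduction sentence is permissive, so the stronger sentence before it may only fix the target level. Read literally, the body text could also undo a reduction on the day it begins, which can hardly be meant. On this view the tables supply the timing on which 5.4.2 is silent. That is probably the intent, but it is not written, and the second-reduction sentence again uses the language of obligation. Table 9 grade 2 is a gap, not a contradiction.

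There are safeguards. The investigator may reduce or stop the drug at any time (5.4.2) and may end treatment when clinically required (8.1). Section 5.4 adds "If dose adjustment is required for other reasons, it is necessary to discuss with the sponsor and make a decision", which may cover re-escalation. No site is locked into a higher dose. None of these provisions says which text governs.

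A reader might also infer that the protocol has no efficacy reason for returning to 150 mg. Section 1.5.2.1.4 does say that reduction to 100 mg does not affect efficacy in a patient who cannot tolerate 150 mg. The bullet before it says that lower doses leave more patients below the exposure threshold. That is a reason to return, though it does not settle the timing.

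On Table 9, the grade 3 or 4 row calls 100 mg the reduced dose and stops treatment if grade 3 or higher recurs. It plainly assumes a patient on 150 mg, so the gap is narrow. Nor does 5.4.2 require every patient on 50 mg with a bilirubin event to stop. It stops only those who need less than 50 mg.

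**Conclusion.** The point holds in two limited parts. First, 5.4.2 and its tables differ on whether re-escalation is required and how long to wait, and no precedence is stated. The difference is up to 28 or 42 days per step, at 1.5 times the dose for a patient moving from 100 to 150 mg. Second, Table 9's fixed 100 mg gives no reduction at 100 mg and reads as a doubling at 50 mg. This affects only patients with an isolated bilirubin event who had already been reduced.

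The timing figures rest on reading the body text literally; a site that treats the tables as the specific rule would see no early re-escalation. How many patients are affected cannot be derived from the documents. A reader might infer a consequence for PFS, the sample size or the consistency criterion, but nothing in the documents supports one. This is a dosing-instruction defect that should be corrected because correction is cheap and bears on patient safety.

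**What to change.** Add one sentence to 5.4.2: restart dose and timing of re-escalation follow Tables 6, 7, 9 and 10; re-escalation is optional; the body text sets only the maximum level to which a patient may return.

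Replace the fixed restart in both Table 9 rows with: resume one dose level lower (100 mg if on 150 mg, 50 mg if on 100 mg); never restart above the dose at onset; if on 50 mg, resume at no more than 50 mg, or discontinue under 5.4.2 if a dose below 50 mg is needed.

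The cost is amendment wording and a memo to sites, with no extra patients or procedures. The downside is that some patients will stay 28 to 42 days at a lower dose, where the protocol's model puts slightly fewer above the exposure threshold (87.9% at 100 mg against 93.6% at 150 mg).

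### Table 6, Grade 3 row: read literally, ripretinib may be restarted at a reduced dose after 7 days with the skin, joint or muscle toxicity still at Grade 3; recovery first was probably meant but is not stated

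*Combined protocol and SAP*

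**What the plan says.** Table 6 (protocol Section 5.4.2) governs ripretinib dosing for skin toxicity except alopecia and for joint pain or myalgia. For Grade 3 it gives supportive treatment and then: "Withhold DCC-2618 for at least 7 days or until the event resolves to grade 1 or baseline level (28 days at most". The restart instruction follows directly, with no condition on grade: "28 days at most). Resume DCC-2618 at a reduced dose". The row ends by allowing re-escalation by one dose level if the event has stayed at grade 1 or baseline for at least one 42-day cycle after the reduction.

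Two general rules sit around the table. Section 5.4 limits the length of any interruption: "If dose interruption is more than 28 days, treatment with the study drug will be terminated in this patient". Section 5.4.2 adds a non-recovery rule that opens "If an AE leads to dose adjustment and is not recovered to grade 1 or baseline level within 1 cycle (42 days" and requires discontinuation, unless the investigator considers the event not clinically significant. In that case, resuming at a reduced level is judged after consulting the sponsor.

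**The concern.** The hold ends when either of two conditions is met: 7 days have passed, or the event has resolved. A site that holds for 7 days and restarts at 100 mg with the event still at Grade 3 has followed the row. A site that waits for recovery has also followed it. Two sites can therefore treat the same event differently, and one of them re-exposes a patient to the drug while a severe toxicity continues.

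The protocol's general severity scale (Section 7.2) describes Grade 3 as severe or medically significant. From Cycle 3, Table 1 schedules visits only on Day 1 of each 42-day cycle, so a day-7 restart need not fall on a planned assessment of grade. What is at stake is the clarity of a safety instruction. The primary PFS analysis, the sample size and the planned safety tables are not touched.

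**Working it through.** The check is mainly textual: does any rule supply the missing recovery condition, and how do neighbouring rows treat restart?

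**1. Logic of the row.** As written, restart is allowed if (hold ≥ 7 days) OR (event at grade 1 or baseline), with hold ≤ 28 days. A patient still at Grade 3 on day 7 meets the first limb. If recovery were required, the rule would be (hold ≥ 7 days) AND (event at grade 1 or baseline), with hold ≤ 28 days.

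**2. Restart conditions side by side (all Section 5.4.2).**

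| Place | Condition for restart |
|---|---|
| Table 6, Grade 3 | 7 days or recovery; the restart line itself has no condition |
| Table 6, Grade 2, once drug is stopped | Recovery: "If the event is recovered to grade 1 or baseline level after 7 days, DCC-2618 will be resumed at a reduced dose level" (same dose if recovered within 7 days) |
| Table 9, bilirubin, Grade 3 or 4 | Recovery: "Interrupt DCC-2618 until toxicity resolves to Grade 1 or baseline (maximum 28 days); otherwise permanently discontinue DCC-2618"; the Grade 2 row also requires it |
| Table 10, general Grade 3 or 4 row | Recovery: "Discontinue DCC-2618 until the event is relieved to grade 1 or baseline level" |
| Table 7, Grade 3 hypertension | Stop only if symptomatic, so dosing at Grade 3 is expressly possible |
| Table 10, asymptomatic or not clinically significant Grade 3 or 4 laboratory abnormality | Continue at first; a longer-lasting Grade 4 may resume at Grade 3; stated expressly |

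Recovery to grade 1 is thus not a universal rule. But the last two rows, where dosing at Grade 3 is accepted, say so and tie it to absence of symptoms or of clinical significance. Table 6 says nothing of that kind.

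**3. Does another rule close the gap?**
- Table 10 does not. Its title limits it to reductions "due to treatment-related adverse events not mentioned above", which excludes Table 6 events.
- Section 5.4 does not. It limits the length of the hold, not the grade at restart.
- The 42-day rule acts only later. From a day-7 restart it forces a stop after at most 42 − 7 = 35 days if the 42 days run from the start of the hold, or 42 days if they run from the dose reduction; the starting point is not stated. The interval is shorter if the site re-applies the row and holds again.
- Advance discussion of a dose reduction with the sponsor is required only as far as possible.

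**4. Size.** The ripretinib arm has 49 planned patients. The text available for review gives no Grade 3 rate for rash, arthralgia or myalgia. Second-line arthralgia at 150 mg in the phase 1 study (Table 3) was 9/31 = 29.0%, not split by grade. Purely as an assumption, a Grade 3 rate for Table 6 events of 1%, 5% or 10% gives 49 × 0.01 = 0.49, 49 × 0.05 = 2.45 or 49 × 0.10 = 4.9 patients reaching this row. Those restarted while still at Grade 3 would be a subset of that number, and nothing in the documents lets it be estimated.

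**The case against.** The strongest reply is that no sensible investigator would read the row this way. A phrase beginning 'at least' sets a floor and does not trigger a restart. The 28-day maximum has little purpose unless the hold is meant to run to recovery. The re-escalation line presupposes that the event has come down to grade 1 or baseline. A patient restarted at Grade 3 would meet the same row again and be told to withhold. All of this stands as evidence of intent, and it is why recovery first is the likelier meaning. It does not make the early restart non-compliant.

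A second reply is that a timed hold with a mandatory dose reduction may have been deliberate, since Section 5.4.2 contemplates adjusted dosing while an event stays unrecovered for up to 42 days. That cannot be excluded. If so, the row still needs to say at what grade restart is acceptable.

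A third is that protections exist. The investigator may reduce or stop at any time (Sections 5.4.2 and 8.1). Grade 4 events and Stevens-Johnson syndrome or hypersensitivity lead to discontinuation. The 42-day stop can be waived only for an event considered not clinically significant, with sponsor consultation before resuming, and a persisting Grade 3 event would rarely qualify. This stands too, and it keeps the point minor.

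**Conclusion.** The ambiguity is real and the point is a cheap improvement to a patient-safety instruction. The Grade 3 row permits a reduced-dose restart after 7 days without recovery, and no other rule prevents it at that moment. The number affected is unknown and probably small; the 1% to 10% range is an assumption and counts patients reaching the row only.

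A reader might infer three stronger things that the documents do not support:
- That the protocol directs re-dosing at Grade 3. It permits this, does not order it, and probably did not intend it.
- That Grade 3 events are managed more loosely than Grade 2 overall. Only the restart condition is looser; Grade 3 brings an immediate hold and a mandatory reduction, whereas Grade 2 starts with continued dosing.
- That patients are left unprotected or that the trial's results are at risk. The backstops are partial but real, and no efficacy or safety analysis depends on this row.

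**What to change.** Change the connective and tie the restart to resolution. For example: *withhold for at least 7 days and until the event is back to grade 1 or baseline (28 days at most; if not resolved, discontinue per Section 5.4); after resolution, resume at a reduced dose.* This keeps the sponsor's 7-day term. The day-28 stop is no new limit: once recovery is required, an unresolved event would run past the interruption maximum already in Section 5.4.

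The cost is one line in Table 6 and a memo to sites. Some patients would be held longer, including any who recover before day 7 and could now restart sooner. A patient improved only to Grade 2 by day 28 would stop study drug, where the present wording allows a reduced-dose restart. The sponsor should also compare the matching row in INTRIGUE, because Section 1.5.1 describes the two designs as similar; that row cannot be seen from these documents.

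If a timed hold was intended, keep it, say so, and state the highest grade at which restart is allowed.

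### Table 7 lets ripretinib held for symptomatic Grade 3 hypertension restart at the same dose when only one blood-pressure component is at target

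*Combined protocol and SAP*

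**What the plan says.** Table 7 in section 5.4.2 governs ripretinib dosing in hypertension. Its Grade 3 row has two pressure limbs joined by *or*, "Systolic blood pressure ≥ 160 mmHg" and "or diastolic blood pressure ≥ 100" mmHg, plus a third limb based on how much antihypertensive treatment is needed.

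For a Grade 3 patient the row does the following:

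- It sets an antihypertensive target of diastolic "pressure ≤ 90 mmHg or systolic blood pressure ≤140 mmHg". The Grade 2 target is worded the same way: diastolic "pressure ≤ 90 mmHg or systolic blood pressure ≤ 140 mmHg".
- It interrupts ripretinib only in symptomatic patients, with this release rule: "If symptomatic, DCC-2618 should be discontinued until diastolic blood pressure ≤ 90 mmHg and/or systolic blood pressure ≤ 140 mmHg and symptom resolved".
- It then fixes the restart dose: "DCC-2618 is resumed at the same dose level".
- It adds a later step: "If BP is uncontrollable after adding new drug or more intensive treatment, DCC-2618 will be reduced by a dose level". No threshold is given for uncontrollable.

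Section 5.4 caps any hold: "If dose interruption is more than 28 days, treatment with the study drug will be terminated in this patient".

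**The concern.** A hold rule should prevent restart until the condition that prompted the hold is under control. This row asks for two things before restart, symptom resolution and a pressure condition. Joining the two pressure components with *and/or* means that either one satisfies the pressure condition, however high the other is. A patient who has already had symptoms from Grade 3 hypertension on ripretinib can then go back on the full current dose with one component still in the Grade 3 range.

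The stake is the safety of ripretinib-arm patients. Hypertension is an expected event on this drug. In addition, Table 1 schedules vital signs from Cycle 3 onward only on Day 1 of each 42-day cycle, so after a restart the next scheduled reading could be weeks away, although unscheduled checks are allowed.

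**Working it through.** The protocol states no figure to reproduce here. The check applies the row's own rules to specific readings.

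**Rules, symptoms taken as resolved**

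- Grade 3 by pressure: SBP ≥ 160 or DBP ≥ 100.
- Current release: DBP ≤ 90 or SBP ≤ 140 (*and/or* is met by either alone).
- Proposed release: DBP ≤ 90 and SBP ≤ 140.

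| Reading | Grade 3 by pressure? | Current rule | Proposed rule |
|---|---|---|---|
| 178/88 | Yes (178 ≥ 160) | Restart (88 ≤ 90) | Hold |
| 138/102 | Yes (102 ≥ 100) | Restart (138 ≤ 140) | Hold |
| 138/88 | No | Restart | Restart |
| 150/95 | No | Hold | Hold |

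The current rule releases two patients who are still Grade 3 and holds one, at 150/95, who is not. Under the proposed rule the highest reading that passes is 140/90, so no patient who is Grade 3 by pressure can restart.

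**Comparison with the Grade 2 row.** A Grade 2 hold for a symptomatic diastolic rise ends when symptoms clear and diastolic is at or below 90. A reading of 138/102 fails that release but passes the Grade 3 one. On that reading the more severe event has the easier restart.

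**A second ambiguity.** The sentence can also be parsed as diastolic at target, and/or systolic at target with symptoms resolved. Read that way, a diastolic of 90 or less would allow restart before symptoms clear. Using *and* throughout removes this reading too.

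**Other rules that might block the restart**

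- Dose reduction for uncontrollable pressure (Table 7): no threshold is defined, and because the row's treatment target also uses *or*, 178/88 arguably counts as at target.
- 28-day limit (section 5.4): it caps the length of a hold and sets no pressure for restart.
- 42-day rule (section 5.4.2): ripretinib stops if an event that led to dose adjustment has not returned to Grade 1 or baseline within a cycle. It acts late and has an exception for events judged not clinically significant. Section 5.4 also explains dose adjustment as dose reduction, so a hold followed by a same-dose restart may not trigger it.
- Table 10, general Grade 3 or 4 row: it requires return to Grade 1 or baseline and a lower dose, but the table covers only events not dealt with in the earlier tables.
- Investigator discretion (section 5.4.2): it allows a longer hold but does not require one.

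**Number of patients.** The phase 1 adverse-event table (Table 3) gives all-grade hypertension at 150 mg QD as 28/142 (19.7%) overall and 8/31 (25.8%) in second line. Applied to 49 ripretinib patients:

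- 28/142 × 49 = 9.7
- 8/31 × 49 = 12.6

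This is an outer ceiling, because it counts every grade. Assuming that 5% to 25% of these reach symptomatic Grade 3 (not in the documents):

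- Low end: 9.7 × 0.05 = 0.5
- High end: 12.6 × 0.25 = 3.2

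So about 0.5 to 3 patients would be held under this row. Those with one component at target and the other still Grade 3 when symptoms clear are a subset, which the documents give no data to size.

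**The case against.** The best counter-argument is that symptoms, not pressure, trigger this hold. A Grade 3 patient who never had symptoms stays on ripretinib with antihypertensives, so a held patient at 178/88 whose symptoms have cleared is back in a state the table already tolerates. That is a fair account of the table. It does not explain why the row adds a pressure condition to symptom resolution and then lets one component satisfy it, and these patients have already shown symptoms on the drug.

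A second argument is that *and/or* may mean that whichever component was raised must come back to target, so that 178/88 would not end a systolic hold. That may be what was intended, but the text does not say it.

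Third, the protocol is not uniformly stricter elsewhere. Table 9 (Grade 3 or 4 bilirubin) and the general row of Table 10 require Grade 1 or baseline and a reduced dose. Another Table 10 row, however, lets an asymptomatic Grade 4 laboratory abnormality restart at Grade 3, possibly at the current dose. This weakens the comparison, though that row concerns laboratory values without symptoms. It can also be argued that the 42-day rule does reach holds, since Table 7 itself presents them as dose adjustment. Even so, the rule acts after the restart.

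Fourth, requiring both components at target also keeps a patient at 150/85 on hold. That reading is Grade 2 by pressure, and the Grade 2 row would generally continue treatment. This cost is real and stands. Requiring only that neither component remain Grade 3 would be the narrower change, but 140/90 are the thresholds the row itself chose.

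Finally, the text permits an early restart and does not compel one, and few patients are involved. Both points are accepted.

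**Conclusion.** The concern holds. As written, the Grade 3 row allows a same-dose restart in a symptom-free patient who still meets the row's own pressure definition of Grade 3, and no other provision requires both components to be at target first. The point applies only to ripretinib patients already held for symptoms; Grade 3 patients who were never symptomatic are outside it.

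The logical result needs no assumption beyond reading *and/or* literally. The headcount does: roughly 0.5 to 3 held patients rests on the assumed 5% to 25% share, and the number actually exposed is smaller and could be zero. The primary analysis and sample size are unaffected. It should be corrected because it concerns patient safety and the remedy is cheap.

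**What to change.** - In the Grade 3 release condition of Table 7, replace *and/or* with *and*: diastolic ≤ 90 mmHg and systolic ≤ 140 mmHg and symptoms resolved.
- Change *or* to *and* in the Grade 2 and Grade 3 antihypertensive targets, so that treatment aims at the same pressures that release the hold.
- State that restart is judged on pressure and symptoms, not on the number of antihypertensives. Otherwise a patient well controlled on two drugs could be barred by the treatment-intensity limb of Grade 3.
- Leave the Grade 2 diastolic-triggered hold as it is, because its release already matches its trigger.

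The cost is a wording amendment to one table, with no added visits or tests. Some holds will last longer, and a few may reach the 28-day limit in section 5.4, at which point study drug is terminated.
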